7.0 Procedures Involved*

7.1.1 Description of research procedures

Approach: We will explore the acceptability, feasibility, and potential efficacy of BWL exposure to treat CRCI in survivors of autologous or allogeneic HSCT. The proposed approach will be informed by procedures [name] developed for her recent research on BWL treatment of CRF in breast cancer patients undergoing chemotherapy. We will recruit study participants and oversee use of the light boxes, monitoring equipment, assessment scales, and enter adherence and actigraph data. We will also determine the feasibility of assessing levels of inflammatory immune markers (i.e., Interleukin-1 receptor agonist [IL-1ra], interleukin-6 [IL-6], interleukin-8 [IL-8], interleukin-10 [IL-10], soluble tumor necrosis factor receptor type II [sTNF-RII], soluble intercellular

PROTOCOL TITLE: Treating cognitive impairments in cancer patients via systematic light exposure

adhesion molecule-1 [sICAM-1], C-reactive protein [CRP], peripheral blood mononuclear cells [PBMCs], and intracellular RNA) as mediators of the clinical impact on cognitive functioning.

Methods: Potential participants will be identified via the Northwestern University Enterprise Data Warehouse service (EDW) and available transplant database from the transplant team after providing them with a list of inclusion and exclusion criteria for the study. The IRB number for that protocol is STU00012731. A query of eligible patients and their physicians will then be created for the research staff. The research study staff will also review their EMR to ensure initial eligibility. The study team member will then contact the treating physicians to request permission to contact their patient(s) about the study. An attempt will be made, via an email sent by the study team member to the physician on in-person, to request permission to contact their patient(s). If the physician authorizes contact be made, research staff will contact the patient to gauge whether or not they are interested in participating in the study. Following physician approval, initial contact will be made with the patient (potential participant) either in-person at their next clinic appointment, or (e)mailed a recruitment letter with a study brochure attached (if their next clinic appointment is over a month away). For in-person recruitment, the study team member will approach patients at their next medical appointment at Northwestern Medicine (identified by the medical database). For letter recruitment, the study team member will inform them that a) they will be contacted in the near future about a research study and b) instructions on what to do if they do not wish to be contacted further. Those potential participants who do not opt-out of further contact will be contacted by the research study staff via preferred method as indicated in their EMR (via telephone, mail, etc.)

We will also use a community recruitment method. For this method, participants will be recruited through:

- 1) HCST and hematological malignancy groups - We will obtain permission from support group facilitators and advocacy organizations to have members of our study team (PI and/or research staff member) to attend and/or disseminate information about the study (flyers and brochures)
- 2) Online listservs and websites for patient advocacy – After obtaining permission as necessary, we will post information about the study to these online listservs and websites (flyers)
- 3) Local oncologists who think their patients might be interested in participating in the study – We will approach local oncologists and request permission to disseminate and/or post information about the study (flyers and brochures).

The study team member will then contact patients who express interest in the study or respond to recruitment solicitations.

The study team member can then describe the study (either in-person or by phone) to determine their interest in participating. Consent can be obtained either in-person or by phone and the screening scheduled. Participants who self-refer (i.e. contact study staff directly after learning about the project through a support group, their oncologist, or another source) will also undergo the Northwestern University verbal consent via phone call.

PROTOCOL TITLE: Treating cognitive impairments in cancer patients via systematic light exposure

After obtaining consent, the screening interview will be undertaken which includes the completion of questionnaires based on inclusion/exclusion criteria as listed in Section 3.0.

If the patient decides not to participate in the study, the research assistant will ask if he/she will complete the refusal questionnaire consisting of their age, ethnicity, type of transplant, time since transplant and time since diagnosis. The information collected by the refusal questionnaire will help inform the study team on what kinds of barriers to participation potential participants may have. If a patient does not want to fill out the refusal questionnaire, they will not be required to and will be thanked for their time. The suicidality protocol will be in place throughout the entire study (see Section 9.1.2).

Those who are screened to meet inclusion criteria will be invited to participate in the main intervention study. At their first appointment (described below), the study team member will take the participant through the written consent form which also requires HIPAA approval permitting access to their medical records. Participants who self-refer (i.e. contact study staff directly after learning about the project through a support group, their oncologist, or another source), will undergo the written consent/HIPAA approval process at Northwestern University, and will also sign a Northwestern University consent form. They will be provided a release of information form to provide study staff permission to contact their physician(s) for information in his/her medical records. Participants will be randomly assigned to BWL or DRL. Participants in both intervention arms will be assessed one week before the intervention (baseline), during the intervention (2 weeks into the intervention), at the end of the intervention (during the fourth week), and two months post-intervention at Northwestern Medicine.

Time 1 Assessment

Participants will answer interview questions about their background, complete questionnaires via RedCap, have blood drawn by a trained phlebotomist, and undertake a brief neuropsychological assessment. Participants will have the choice to complete questionnaires from home via RedCap prior to their visit via a link that will be sent to them by email. Actigraphy measurement will occur following the neuropsychological assessment and completion of questionnaires. It requires the participant to wear the actigraph for 7 consecutive days and complete a sleep log on which they will record time to bed, time awake and other information to be used in editing and scoring the data.

Description of Light Treatment (including Litebook)

Following the Time 1 assessment, participants will be instructed to self-administer light treatment for 30 minutes every morning for 4 weeks. Participants will be informed that "The Litebook is a compact portable lamp (approximately 5" x 5" x 1") and weighs less than a pound. It is very easy to use. The Litebook is directed toward the eyes for 30 minutes each morning in order to trigger light receptors in the retina to trigger a cascade of messages throughout the body. It is powered by a rechargeable lithium-ION battery which we provide and can also be connected to a power source." As indicated in the consent form, participants will be told that they will receive one of two different light boxes of different wavelengths that are being tested (i.e., the same light box but with different bulbs to emit different wavelengths). The 30 minute dose is used in the treatment of seasonal affective disorder and has been shown to have a low risk of side-effects. For participants who require assistance, we will work with a caregiver to ensure correct actigraph and light box

PROTOCOL TITLE: Treating cognitive impairments in cancer patients via systematic light exposure

use. The assessment schedule and data analytic plan will allow us to address the Specific Aims. To increase the likelihood of adherence, email reminders will be sent to participants to use the light boxes and complete sleep and Litebook logs.

Litebook devices can only emit one wavelength – either BWL or DRL – but they are identical in all other ways. BWL Litebook emits approximately 1000 lux and the DRL Litebook emits < 50 lux. Safety precautions are the same for both as indicated by the research outlined below.

Use of Litebook in Previous Research

[name] and colleagues' (2014) investigated BWL to treat cancer-related fatigue in cancer survivors (including HSCT) using the same Litebooks for the current study. BWL was found to be more effective in reducing cancer-related fatigue than DRL. There were no safety concerns nor adverse events. This study was approved by Mount Sinai's IRB in 2011.

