1.2 Hypotheses

- Hypothesis 1: BWL treatment will be feasible and acceptable in autologous and allogeneic HSCT survivors.
- Hypothesis 2: Auto-HSCT and allo-HSCT survivors receiving BWL will have greater improvement in cognitive functioning than those receiving DRL.
- Hypothesis 3: The relationship between BWL and CRCI will be mediated by CAR and sleep.

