3.0 Inclusion and Exclusion Criteria

3.1 How individuals will be screened for eligibility

The first part of the screening interview can be conducted by phone and internet. It includes questions based on inclusion/exclusion criteria. Participants who meet criteria for entry into the study will be randomly assigned to BWL or DRL. Participants who are ineligible or decline participation will be thanked for their time and informed that they have completed the study.

3.2 Criteria that define who will be included or excluded in final study sample

Eighty autologous and allogeneic HSCT survivors will be recruited at Northwestern University, Feinberg School of Medicine, Department of Medical Social Sciences from Northwestern Memorial Hospital (NMH) and Robert H. Lurie Comprehensive Cancer Center (RHLCCC).

In order to qualify for participation in the study, potential participants must meet the following eligibility inclusion criteria:

1. Have a history of autologous or allogeneic HSCT,
2. Be in at least partial remission and not on active treatment (maintenance chemotherapy is ok),
3. Have less than severe graft-versus-host-disease (GVHD)
4. 1 to 5 years post-HSCT,
5. Age 21 or older,
6. English language proficient
7. Able to provide informed consent
8. Endorse subjective cognitive impairment.

Potential participants will not be allowed to participate in the study if they meet any of the following exclusion criteria:

1. Being treated for, or been diagnosed with or suspected neurological, psychiatric (including bipolar disorder or mania), or medical condition that might impair cognitive functioning (other than those caused by the cancer or its treatment),
2. Visual, hearing, or physical impairment sufficient to interfere with cognitive testing or participation,
3. Have a history of whole brain irradiation or surgery,
4. Active diagnosis of autoimmune and/or inflammatory disorder or disorders that may influence immune processes,
5. Have a history of severe graft-versus-host-disease
6. History of systematic light exposure treatment,
7. Diagnosed sleep apnea or narcolepsy,
8. Use of photosensitizing medications (including antibiotics that render participants photosensitive),
9. Plan to travel across meridians during the study,
10. Work night, early morning, or swing shifts,

PROTOCOL TITLE: Treating cognitive impairments in cancer patients via systematic light exposure

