11. Adults unable to consent, individuals who are not yet adults, pregnant women and prisoners will be excluded from the study.
12. History of eye disease including, but not limited to, macular degeneration.
13. Undergone laser corrective eye surgery in the past 30 days.

The excluded conditions have been chosen due to their known impact on cognitive function, the biomarkers to be studied, or are contraindications for light treatment.

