4.0 Study-Wide Number of Subjects

Eighty autologous and allogeneic HSCT survivors will be recruited at Northwestern University, Feinberg School of Medicine, Department of Medical Social Sciences from Northwestern Memorial Hospital (NMH) and Robert H. Lurie Comprehensive Cancer Center (RHLCCC).

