17.2 Other resources available to conduct the research

Northwestern completes approximately 180 autologous and approximately 54 allogeneic transplants per year. Based on these numbers, there will be more than sufficient numbers of HSCT survivors available to screen 227 across 48 months of recruitment.

We have wet and dry labs available to undertake all assessments with participants in the Biopsychosocial Mechanisms and Health Outcomes Program. The dry lab is located on the 19th floor of [name] and includes a blood draw room and assessment suites. The wet lab is located in the Lurie Research Building with an on-site lab technician who will take care of the processing and storage of biospecimens prior to distribution to the Evanston campus for analysis. The Northwestern Clinical Research Unit CORE laboratory is located in the Feinberg Hospital building of Northwestern Memorial Hospital with on-site lab technicians who will take care of the processing and storage of biospecimens depending on the availability of wet lab staff (i.e. CORE lab will process if BMHO wet lab staff is not available).

This is a minimal risk study. However, we will have contact information for any participant's physician and the transplant team's social worker on hand should any medical or psychological issues arise.

All persons assisting in the research will be rigorously trained by the PI in the procedures from recruitment, to assessments, to how to deal with unanticipated adverse events.

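### The protocol specifies no stratification by transplant type, nor any other randomisation method, for a sample that pools autologous and allogeneic survivors

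*Combined protocol and SAP*

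**What the plan says.** Allocation is described in two near-identical sentences. Section 3.1: "Participants who meet criteria for entry into the study will be randomly assigned to BWL or DRL". Section 7.1.1: "Participants will be randomly assigned to BWL or DRL". Neither these sections nor any other names a stratification factor, block size, sequence generation or concealment. A 1:1 ratio is only implied, by the 40 per group used in the power statements of Sections 9.1 and 9.2.

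The sample is pooled. Inclusion criterion 1 in Section 3.2 is "Have a history of autologous or allogeneic HSCT", and Section 4.0 says "Eighty autologous and allogeneic HSCT survivors will be recruited at Northwestern University". Hypothesis 2 (Section 1.2) covers both types in one comparison: "Auto-HSCT and allo-HSCT survivors receiving BWL will have greater improvement in cognitive functioning than those receiving DRL". No quota by type is set. The only guide to the mix is Section 17.2: "Northwestern completes approximately 180 autologous and approximately 54 allogeneic transplants per year".

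The safeguard against imbalance is in the analysis. Section 9.1 compares the arms at baseline with t-tests and Fisher's exact tests on possible confounders, and makes covariates of those that differ. It names time since transplant as one such variable. It does not name transplant type, and it gives no threshold for a difference.

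**The concern.** Transplant type is a natural balancing factor here. It divides the sample into a larger and a smaller group, and it is known before allocation, because transplant history is an eligibility criterion.

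The protocol's own eligibility logic points the same way. Section 3.2 excludes severe graft-versus-host disease and admits milder disease. It explains its exclusions thus: "The excluded conditions have been chosen due to their known impact on cognitive function, the biomarkers to be studied", with contraindication to light as a third reason. If milder graft-versus-host disease is concentrated in the allogeneic group (an assumption; the documents give no rates by type), the split of that group could matter for cognition and for the inflammatory markers.

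At stake is the arm comparison in a trial whose estimate is meant to prepare for a larger one (Section 1.1, Aim 2). If the arms differ in their allogeneic share, part of an observed difference may reflect the mix of types, and a test-driven covariate rule may not pick this up.

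**Working it through.** **Inputs.** N = 80 (Section 4.0); 40 per arm (Sections 9.1 and 9.2); 180 autologous and 54 allogeneic transplants a year (Section 17.2). The recruitment figures in Section 20.1 reproduce: 227 × (1 − 0.119) = 200, and 200 × 0.40 = 80. The detectable difference of 0.209 in Section 9.2 has no stated SD, unit or contrast, so it cannot be reproduced and is not used here.

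**Expected allogeneic count.** 54/234 = 0.231, and 0.231 × 80 = 18.5; 18 is used below.

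**Chance of an uneven split of 18.** Under simple randomisation this is 2 × P(Bin(18, 0.5) ≤ k). For k = 6: 2 × 31180/262144 = 0.238. For k = 5: 2 × 12616/262144 = 0.096. With arms fixed at 40:40 the count in one arm is hypergeometric (18 drawn from 80, 40 in that arm). Fisher's p is the same two-sided tail.

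| Split or worse | Simple | Fixed 40:40 | Fisher p at this split | Difference in allogeneic share |
|---|---|---|---|---|
| 12:6 | 23.8% | 18.0% | 0.18 | 6/40 = 15 points |
| 13:5 | 9.6% | 5.9% | 0.059 | 8/40 = 20 points |
| 14:4 | 3.1% | 1.4% | 0.014 | 10/40 = 25 points |

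**Sensitivity to the inferred count.** Chance that at least two-thirds of the allogeneic patients fall in one arm:

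| Allogeneic patients | Simple | Fixed 40:40 |
|---|---|---|
| 12 | 39% | 35% |
| 15 | 30% | 25% |
| 18 | 24% | 18% |
| 24 | 15% | 9% |
| 30 | 10% | 4% |
| 40 | 4% | 0.3% |

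**Does the baseline rule catch it?** At p < 0.05 (assumed), adjustment starts only at 14:4. At p < 0.10 it would start at 13:5, and at p < 0.20 at 12:6. The plan does not say which applies.

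**Effect on the arm contrast.** Let D be the difference between types in SD units; the documents give none, so 0.2 to 0.8 is assumed.

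- *Level contrast:* shift = difference in share × D. At 12:6 this is 0.15 × D = 0.03 to 0.12 SD; at 13:5, 0.20 × D = 0.04 to 0.16 SD. The standard error of a single-visit arm difference is √(2/40) = 0.22 SD.
- *Change contrast:* D becomes the difference between types in change from baseline. If the types differ by a constant amount over time, the shift is zero.
- *Precision:* the share of outcome variance due to type is 0.231 × 0.769 × D², which is 1.6% at D = 0.3, 4.4% at 0.5 and 11.4% at 0.8.

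**After stratification.** With blocks of 4 within the allogeneic stratum, 18 patients split 9:9 about two-thirds of the time and 10:8 otherwise; with blocks of 2 or 6, always 9:9. The largest difference in share is 2/40 = 5 points, and the level shift is at most 0.05 × D = 0.01 to 0.04 SD.

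**Cost of adjusting.** The squared correlation between arm and type is (a − b)²/(18 × 62) for a split a:b. At 13:5 it is 64/1116 = 0.057, a variance inflation of 1/(1 − 0.057) = 1.06. At 10:8 it is 4/1116 = 0.004, so adjustment costs almost nothing once the arms are balanced.

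**The case against.** The strongest reply is that the consequence is small. Hypothesis 2 concerns improvement, and cognition is tested at Times 1, 3 and 4 in a repeated-measures model. Markers also have a baseline draw. A stable difference between types is present at baseline too and drops out of a group-by-time contrast. To shift that contrast, the types would have to change differently over the study, and nothing in the documents suggests that they do. Even on a level contrast, a 13:5 split at D = 0.5 shifts the result by 0.10 SD, under half a standard error, and chance imbalance is already within what the standard error covers. The efficacy aim is preliminary and the marker aim exploratory. All of this stands, and it limits the point.

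It does not remove it. Section 9.1 says only that contrasts compare the groups across assessments, which does not settle whether level or change is tested. Treatment satisfaction, measured once after the intervention and compared by t-test, is plainly a level contrast.

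It can also be said that Section 9.1 already covers this, since transplant type is a clinical characteristic. That reading is fair, but type is not named and adjustment depends on a test with no stated threshold.

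Three stronger inferences are tempting and not supported:

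- A reader might take the wording as a decision for simple, unstratified randomisation. The documents are silent on method; they do not rule stratification out.
- A reader might conclude that the efficacy result will be biased by 0.10 SD or more. That needs an uneven split, an assumed difference between types and a level contrast, all together.
- A reader might expect allogeneic patients to have worse cognition or higher inflammatory markers. The documents give no such figures, and Section 3.2 excludes severe graft-versus-host disease and active immune or inflammatory disorders, which would narrow any difference.

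**Conclusion.** The gap is real and modest. No randomisation method is specified, so nothing in the text protects the balance of transplant type. With 18 allogeneic patients, a 12:6 or worse split would arise in about one trial in four (simple) to one in six (fixed 40:40), and 13:5 or worse in about one in ten to one in seventeen. The stated covariate rule would miss both at p < 0.05.

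This is chance imbalance and lost precision, not systematic bias. It matters mainly for level contrasts, or if the two types change differently over the study.

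The conclusion rests on three assumptions: that enrolment follows site volumes, which community recruitment and the exclusions could alter; the 0.05 threshold; and the between-type difference, for which the documents give no figure.

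**What to change.** In Sections 3.1 and 7.1.1, state that participants are randomised 1:1 to BWL or DRL in permuted blocks of varying size, stratified by transplant type (autologous, allogeneic). This also supplies the missing ratio and blocking; how the sequence is generated and concealed should be stated in the same place.

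In Section 9.1, pre-specify transplant type and its interaction with time as covariates in the Aim 2 and marker models, whatever the baseline test shows. The interaction is needed because a main effect of type alone absorbs only a constant difference and does not protect a group-by-time contrast.

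The cost is a two-stratum list, a few lines of text and a few model degrees of freedom: one for type, plus two for its interaction over the three neuropsychological visits or one over the two blood draws. Sample size and visits do not change.

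The change does not make a conclusion specific to allogeneic patients viable; about nine per arm remains too few for that, and Hypothesis 2 should be read as a statement about the pooled sample.

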Time 4 (8 weeks after the intervention) – The study team will send the actigraph and sleep logs to participants again 7 weeks after the intervention. During the eighth week after the intervention, the participant will be asked to wear the actigraph again for 7 days and complete sleep logs. Then the participant will be asked to come in to Northwestern Medicine again to complete the same procedures as at Time 2, except their blood will not be drawn at this appointment.

Note that the neuropsychological testing portion of each assessment will be audio recorded with the permission of the participant to optimize scoring accuracy by the study team. Participants can still participate in the study even if they choose not to be recorded.

Data about subjects will be collected from medical charts, interview questions, questionnaires that the participants will be administered in-person and via online portal (RedCap), output from the equipment (i.e., actigraph data), and blood samples. All questionnaire data collected through RedCap will be coded to each subject's unique study ID. RedCap will not collect any identifiable information and will not log the participants' IP addresses. Neuropsychological testing will be audio-recorded when permission is given by the participant, and those audio files will also be coded to each subject's unique study ID.

Subjects who wish to receive feedback about their neuropsychological test scores may receive a debriefing from the PI at the end of their participation upon request.

